11.2. Secondary Efficacy Measures

Secondary efficacy measures include other measures of renal function. These include other measures of proteinuria (e.g., uPCR) and measures of glomerular filtration rate. Categorical achievement of treatment response and different levels of proteinuria will also be assessed. The persistence of these proteinuria milestones will also be evaluated.

Secondary efficacy measures include:

- 24-hour UPE (achievement of complete or partial proteinuria remission defined as 24-hour UPE of < 0.3 g or < 0.6 g, respectively)
- uPCR and 24-hour uPCR
- eGFR
- Use of rescue therapy

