### Tertiary Endpoints

- Change from baseline in log-transformed 24-hour uPCR over time in patients in the high-risk proteinuria group (baseline 24-hour UPE  $\geq 2$  g/day)
- Achievement of  $\geq 50\%$  reduction from baseline in 24-hour UPE at 36 weeks in patients in the high-risk proteinuria group (baseline 24-hour UPE  $\geq 2$  g/day)
- Achievement of  $\geq 30\%$  reduction from baseline in 24-hour UPE at 36 weeks in patients in the high-risk proteinuria group (baseline 24-hour UPE  $\geq 2$  g/day)
- Change from baseline in log-transformed 24-hour uPCR over time in patients in the all-patients population (baseline 24-hour UPE  $> 1$  g/day)
- Achievement of  $\geq 50\%$  reduction from baseline in 24-hour UPE at 36 weeks in patients in the all-patients population (baseline 24-hour UPE  $> 1$  g/day)
- Achievement of  $\geq 30\%$  reduction from baseline in 24-hour UPE at 36 weeks in patients in the all-patients population (baseline 24-hour UPE  $> 1$  g/day)
- Time averaged change from baseline in the log-transformed 24-hour uPCR through 36 weeks in patients in the high-risk proteinuria group (baseline 24-hour UPE  $\geq 2$  g/day)
- Achievement of partial proteinuria remission defined as 24-hour UPE  $< 0.6$  g at any time post baseline in patients in the high-risk proteinuria group (baseline 24-hour UPE  $\geq 2$  g/day)
- Achievement of complete proteinuria remission defined as 24-hour UPE  $< 0.3$  g at any time post baseline in patients in the high-risk proteinuria group (baseline 24-hour UPE  $\geq 2$  g/day)
- Time averaged change from baseline in the log-transformed 24-hour uPCR through 36 weeks in patients in the all-patients population (baseline 24-hour UPE  $> 1$  g/day)

- Achievement of partial proteinuria remission defined as 24-hour UPE  $< 0.6$  g at any time post baseline in patients in the all-patients population (baseline 24-hour UPE  $> 1$  g/day)
- Achievement of complete proteinuria remission defined as 24-hour UPE  $< 0.3$  g at any time post baseline in patients in the all-patients population (baseline 24-hour UPE  $> 1$  g/day)
- Use of rescue therapy for IgAN at any time post baseline in patients in the all-patients population (baseline 24-hour UPE  $> 1$  g/day) and in patients in the high-risk proteinuria group (baseline 24-hour UPE  $\geq 2$  g/day)

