- Change from baseline in eGFR at 36 weeks in patients in the all-patients population (baseline 24-hour UPE  $> 1$  g/day) and in patients in the high-risk proteinuria group (baseline 24-hour UPE  $\geq 2$  g/day)
- Pharmacokinetics and pharmacodynamics of narsoplimab
- Occurrence of anti-drug antibodies (ADA) and, if present, neutralizing antibodies (Nab)

Exploratory endpoints are:

- Change from baseline in eGFR over time
- Change from baseline in 24-hour UPE over time
- Change from baseline in 24-hour uPCR over time
- Change from baseline in urine albumin/creatinine ratio (uACR) (from spot urine) over time
- Change from baseline in 24-hour uACR over time
- Achievement of  $\geq 50\%$  reduction from baseline in 24-hour UPE at any time post baseline
- Achievement of  $\geq 30\%$  reduction from baseline in 24-hour UPE at any time post baseline
- Duration of treatment response defined as the number of weeks between the first timepoint at which the patient achieves a  $\geq 30\%$  reduction from baseline in 24-hour UPE and the first timepoint at which the patient relapses (a relapse is defined as an increase in 24-hour UPE by  $\geq 30\%$  from the value of the lowest measured post-treatment UPE in a patient whose 24-hour UPE is  $> 1$  g/day)
- Achievement of 24-hour UPE of  $< 0.3$  g/day at 36 weeks (complete proteinuria remission)
- Duration of complete proteinuria remission defined as the number of consecutive weeks with UPE  $< 0.3$  g/day from the first timepoint at which UPE  $< 0.3$  g/day to the first timepoint at which UPE  $\geq 0.3$  g/day

- Duration of partial proteinuria remission defined as the number of consecutive weeks with UPE < 0.6 g/day from the first timepoint at which UPE < 0.6 g/day to the first timepoint at which UPE  $\geq$  0.6 g/day
- 24-hour UPE following retreatment in patients who relapse after treatment
- Change from baseline in the number of red blood cells per high-powered field (RBC/HPF) over time from baseline
- Change from baseline in biomarkers of complement activity and disease pathology in kidneys, serum, plasma, or urine. Biomarkers may include, but not necessarily be limited to:
  - Mannan-binding lectin (MBL) (serum and urine)
  - Complement component 4a (C4a) (urine)
  - C4d (urine)
  - Kidney injury molecule 1 (urine)
  - Neutrophil gelatinase-associated lipocalin (urine)
  - Clusterin (urine)
  - Markers of tubular and glomerular damage
  - Soluble membrane attack complex (urine)
  - Collectin-11 (urine)

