**Figure 2: Overall Type I Error Control for the Primary and Key Secondary Endpoints**

Abbreviations: UPE = urine protein excretion; +ve = P-value  $\leq 0.05$  in a 2-sided test; -ve = P-value  $> 0.05$  in a 2-sided test; g = grams; d = day.

If the primary efficacy endpoint is statistically significant at 5% level in a 2-sided test, then the key secondary endpoint (1), the rate of change in eGFR over 2 years in the high-risk proteinuria group (baseline UPE  $\geq 2$  g/day), will be tested in a two-sided test at 5% level of significance. If the key secondary eGFR endpoint for the high-risk proteinuria group is statistically significant in a two-sided test at 5% level, then the key secondary eGFR endpoint (2), the rate of change in eGFR over 2 years in the all-patients population (baseline UPE  $> 1$  g/day), will be tested in a two-sided test at 5% level.

Testing of other efficacy endpoints will not be subject to type-1 error control and, therefore, will be viewed as supportive.

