The following time-to-event endpoints will be analyzed by the KM method for each treatment group for the FAS population. If calculable, median time with 95% CI will be provided by treatment group. The HR, CI and p-value will be estimated via Cox regression analysis stratified for the randomization strata and with treatment as the sole class factor.

- Duration of treatment response will include patients in the FAS population who achieve  $\geq 30\%$  reduction from baseline in 24-hour UPE only. Patients who respond but do not relapse during the study will be censored at their last date of 24-hour UPE
- Duration of complete proteinuria remission will include patients in the FAS population who achieve 24-hour UPE  $< 0.3$  g/day only. Patients who achieve complete proteinuria remission but whose 24-hour UPE does not increase to  $\geq 0.3$  g/day during study will be censored at the last date of 24-hour UPE
- Duration of partial proteinuria remission will include patients in the FAS population who achieve 24-hour UPE  $< 1$  g/day only. Patients who achieve partial proteinuria remission but whose 24-hour UPE does not increase to  $> 1$  g/day during study will be censored at the last date of 24-hour UPE

Change from baseline in RBC/HPF will be summarized descriptively by treatment group and scheduled visit.

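### SAP 2.9.2.4 analyses duration of partial proteinuria remission at 1 g/day, but both documents define partial remission and its duration at 0.6 g/day

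*SAP*

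**What the plan says.** SAP 2.9.2.4 gives the analysis rule for three duration endpoints, each summarised by Kaplan-Meier and compared by stratified Cox regression. For partial remission the entry rule is "Duration of partial proteinuria remission will include patients in the FAS population who achieve 24-hour UPE $< 1$ g/day only", and the censoring rule is "Patients who achieve partial proteinuria remission but whose 24-hour UPE does not increase to $> 1$ g/day during study will be censored" at the last 24-hour UPE date.

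The endpoint itself is defined in the exploratory lists of SAP 2.1 and Protocol 7.2.5, in the same words: "Duration of partial proteinuria remission defined as the number of consecutive weeks with UPE < 0.6 g/day from the first timepoint" below 0.6 g/day until the first timepoint at or above 0.6 g/day.

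Achievement of partial remission uses the same cut-off. The SAP's tertiary endpoints have "Achievement of partial proteinuria remission defined as 24-hour UPE $< 0.6$ g at any time post baseline", Protocol 7.2.4 agrees, and Protocol 11.2 has "achievement of complete or partial proteinuria remission defined as 24-hour UPE of < 0.3 g or < 0.6 g, respectively".

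The neighbouring complete-remission bullet in SAP 2.9.2.4 reads "Duration of complete proteinuria remission will include patients in the FAS population who achieve 24-hour UPE $< 0.3$ g/day only", which matches its own 0.3 g/day definition.

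**The concern.** One named endpoint has two thresholds: 0.6 g/day where it is defined and 1 g/day where it is analysed. SAP 2.9.2.4 is the only place that says who enters the analysis and who is censored, so the definition in SAP 2.1 does not settle the matter. A programmer working from 2.9.2.4 and one working from 2.1 would produce different results for the same table title, and the choice between them could be made after unblinding.

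The achievement and duration outputs would also disagree with each other. A patient whose lowest UPE is 0.8 g/day would be a non-achiever of partial remission in one table and would contribute a partial-remission duration in another.

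**Working it through.** **1. Thresholds side by side**

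| Element | SAP 2.1 and Protocol 7.2.5 | SAP 2.9.2.4 |
|---|---|---|
| Enters the analysis | UPE < 0.6 g/day | UPE < 1 g/day |
| Clock starts | first UPE < 0.6 g/day | not stated; implied first UPE < 1 g/day |
| Event | first UPE ≥ 0.6 g/day | implied by the censoring rule: UPE > 1 g/day |
| Censored | no return to ≥ 0.6 g/day (implied) | no rise to > 1 g/day |

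For complete remission the two columns agree at 0.3 g/day. Only the partial-remission bullet departs from its definition.

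**2. Is the 1 g/day value supported elsewhere?** Protocol 14.1.10.3 has a below-1 g/day criterion, but it belongs to responder durability, which is based on time-adjusted AUC and is a different endpoint. SAP section 4 (amendments) records no change to the remission threshold.

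**3. What changes for a patient**

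- Lowest UPE from 0.6 to just under 1 g/day: never in partial remission by definition, but admitted by 2.9.2.4.
- UPE falls below 0.6 and later rises to between 0.6 and 1 g/day: an event by definition, no event under 2.9.2.4.
- UPE passes below 1 g/day at one visit and below 0.6 at a later one: the clock starts earlier under 2.9.2.4.
- UPE of exactly 1 g/day: neither enters nor ends remission under 2.9.2.4. The paired definition (< 0.6, ≥ 0.6) has no such gap.

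**4. Illustration of size at one visit.** The documents give no figure to reproduce here.

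Model: ln(UPE) ~ Normal(ln(baseline) + m, SD), so P(UPE < c) = Φ[(ln(c/baseline) − m)/SD].

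Inputs:
- SD 0.80 (planning value) and 0.63 (blinded estimate), from Protocol 14.1.1 and SAP 1.3.1. Both are stated for patients with baseline UPE ≥ 2 g/day.
- Assumed: mean log change m = 0 or ln(0.65) = −0.431.
- Assumed: baseline 1.2, 2 or 3 g/day. At 1.2 g/day the SDs are borrowed from the higher-baseline group.

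Example (m = 0, SD 0.63, baseline 2):
- P(< 0.6) = Φ[ln(0.3)/0.63] = Φ(−1.911) = 2.8%
- P(< 1) = Φ[ln(0.5)/0.63] = Φ(−1.100) = 13.6%
- Difference 10.8 points, ratio 4.8

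| m | SD | Baseline | P(< 0.6) | P(< 1) | Difference (points) | Ratio |
|---|---|---|---|---|---|---|
| 0 | 0.63 | 1.2 | 13.6% | 38.6% | 25.0 | 2.8 |
| 0 | 0.63 | 2 | 2.8% | 13.6% | 10.8 | 4.8 |
| 0 | 0.63 | 3 | 0.5% | 4.1% | 3.5 | 7.6 |
| 0 | 0.80 | 1.2 | 19.3% | 41.0% | 21.7 | 2.1 |
| 0 | 0.80 | 2 | 6.6% | 19.3% | 12.7 | 2.9 |
| 0 | 0.80 | 3 | 2.2% | 8.5% | 6.3 | 3.8 |
| −0.431 | 0.63 | 1.2 | 33.9% | 65.3% | 31.5 | 1.9 |
| −0.431 | 0.63 | 2 | 11.0% | 33.9% | 22.9 | 3.1 |
| −0.431 | 0.63 | 3 | 3.1% | 14.5% | 11.4 | 4.7 |
| −0.431 | 0.80 | 1.2 | 37.2% | 62.2% | 25.0 | 1.7 |
| −0.431 | 0.80 | 2 | 16.7% | 37.2% | 20.5 | 2.2 |
| −0.431 | 0.80 | 3 | 7.0% | 20.2% | 13.2 | 2.9 |

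Differences and ratios are computed before rounding.

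**5. Direction of the change in duration.** Invented UPE values (g/day) at Weeks 12, 24, 30, 36, 48, 72 and 96, with the clock under 2.9.2.4 starting at the first UPE < 1:

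- Patient A: 0.8, 0.5, 0.7, 0.8, 0.9, 1.2, 1.3. Under the definition, Week 24 to 30 = 6 weeks. Under 2.9.2.4, Week 12 to 72 = 60 weeks.
- Patient B: 0.9, 1.1, 0.5, 0.5, 0.5, 0.5, 0.7. Under the definition, Week 30 to 96 = 66 weeks. Under 2.9.2.4, Week 12 to 24 = 12 weeks.
- Patient C: 1.4, 0.8, 0.9, 1.3, 1.4, 1.5, 1.6. Under the definition, never in remission. Under 2.9.2.4, Week 24 to 36 = 12 weeks.

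**The case against.** The strongest reply accepts the contradiction and disputes its reach and weight.

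- *Start and event.* SAP 2.9.2.4 states only an entry rule and a censoring rule. One could keep the start at the first UPE < 0.6 from SAP 2.1 and end at > 1. Duration could then not shorten: patient A would have 48 weeks (Week 24 to 72) and patient B 66 weeks, censored. It is true that start and event are implied. But that hybrid gives no start time to a patient admitted with a lowest UPE of 0.6 to just under 1 g/day, so starting at < 1 is the only reading that works for everyone the rule admits. The hybrid would still not be the defined endpoint.
- *Borrowed SD.* The SDs belong to the ≥ 2 g/day group, and the 31.5-point maximum and the 1.7 minimum ratio both come from baseline 1.2. This stands as a caveat. With baselines 2 and 3 only, the range is 3.5 to 22.9 points and the ratios are 2.2 to 7.6.
- *Single visit.* Entry depends on each patient's lowest value over all visits, which the illustration does not model. This also stands: the figures show scale and do not estimate how many patients would be wrongly admitted.
- *Weight.* The endpoint is exploratory, and SAP 2.9.1 says "Testing of other efficacy endpoints will not be subject to type-1 error control and, therefore, will be viewed as supportive". That limits the consequence but does not make the rule correct.

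**Conclusion.** The concern holds. SAP 2.9.2.4 contradicts the definition of its own endpoint in SAP 2.1 and Protocol 7.2.5. Followed exactly, it yields a duration analysis of time below about 1 g/day under the name of partial remission. That conclusion rests on the text alone.

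The size cannot be fixed from the documents. The one-visit range depends on the assumed mean changes and baselines, on lognormal UPE and, at baseline 1.2 g/day, on a borrowed SD. The effect on duration can go in either direction if the clock starts at the first UPE < 1 g/day, which is the coherent reading of the rule.

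The primary UPE analysis and the key secondary eGFR analyses are unaffected, and achievement of partial remission remains correctly defined at 0.6 g. This should be corrected, but it does not threaten the trial's main conclusions.

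**What to change.** Rewrite the partial-remission bullet in SAP 2.9.2.4 so that it:

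- includes FAS patients who achieve 24-hour UPE < 0.6 g/day, with the clock starting at the first such value;
- counts the event at the first subsequent 24-hour UPE ≥ 0.6 g/day;
- censors patients who do not return to ≥ 0.6 g/day at their last 24-hour UPE date.

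If an analysis at 1 g/day is wanted as well, list it in SAP 2.1 as a separate, separately named endpoint, with its start, event and handling of exactly 1 g/day stated.

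The cost is one bullet of SAP wording, with no new data. It should be made before database lock.

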#### 2.9.2.5. Exploratory Efficacy Analyses

Subgroup analyses for the primary efficacy endpoint and the two key secondary efficacy endpoints will be performed. The statistical method of the primary analysis for each of the endpoints will be used to analyze the following subgroups by including subgroup factor and treatment by subgroup interaction factors in the analysis model:

- Baseline 24-hour UPE level ( $< 2$  g/day and  $\geq 2$  g/day)
- Baseline eGFR level ( $\geq 30$  to  $\leq 45$  mL/min/1.73 m^2 and  $> 45$  mL/min/1.73 m^2)
- Duration of IgAN diagnosis ( $\leq 2$  years and  $> 2$  years from randomization)
- Sex (Female and Male)
- Race (White and others)
- Age ( $< 65$  and  $\geq 65$ )

#### 2.9.3. Pharmacokinetic, Pharmacodynamic and Immunogenicity Analysis

Blood samples will be collected from patients at intervals using sparse sampling to enable population PK analyses. Biomarker, ADA, Nab, and PD data will be summarized descriptively. An exploratory evaluation of other relevant biomarkers may be conducted.

#### 2.9.4. Safety Analyses

All safety analyses will be descriptive in nature (Section 3.4).

#### 2.9.5. Timing of Planned Analyses

The IDMC will operate in accordance with the IDMC charter and have regular meetings in person or by teleconference. A description of the frequency and nature of IDMC data monitoring and any operating procedures to maintain study blinding are detailed in the IDMC charter.

A blinded SSRE was planned and executed for the primary UPE endpoint. A CP-based SSRE for the key secondary endpoint of eGFR rate of decline in the high-risk proteinuria group is planned at the time of the formal analysis of the primary UPE endpoint in the same population with N = 180 patients. At this SSRE, no formal statistical testing will be performed on eGFR the data.

A formal interim analysis is planned for the primary UPE endpoint. The interim database will include the first 180 patients in the high-risk proteinuria group through 36 weeks in the FAS population. The primary and secondary UPE endpoints will be analyzed and formally tested for treatment comparisons. Other efficacy endpoints will also be descriptively summarized. No formal statistical tests will be performed for the other efficacy endpoints based on the interim database. Safety analyses will be performed. Study sites and patients will remain blinded to the treatment assignment. The study will be unblinded at the study level only so that statistical analyses can be performed. At the time of the formal interim analysis of the primary UPE endpoint in the high-risk proteinuria group, if a treatment effect is proven statistically, the data may be used to support regulatory filings for approval.

The final database lock will occur when all randomized patients have completed the study. The rate of change in eGFR will be estimated and formally tested for treatment comparison if the primary UPE endpoint is statistically significant at the interim analysis. Other efficacy endpoints will also be descriptively summarized. Safety analyses will be performed.

#### 2.9.6. Blinded Sample Size Re-Estimation for Primary Efficacy Endpoint

A blinded sample size re-estimation for the original primary efficacy endpoint was performed by the independent data monitoring committee (IDMC) when 168 patients (60% of 280) had completed the Week 36 visit. A bias-adjusted variance of the log-transformed 24-hour UPE change from baseline to Week 36 was calculated using the pooled variance from the available data and the assumed treatment effect size in a blinded fashion. The bias-adjusted variance was expressed as [Kieser 2003]:

$$\text{VVV}^2 = \text{VVV}^2 - \frac{\Delta^2}{4(m-1)}$$

where  $\text{VVV}^2$  is the pooled variance, n is half of the number of patients with UPE at Week 36 at the time of the sample size re-estimation (*i.e.*, m = 168) and  $\Delta$  is the assumed treatment effect size in the sample size calculation. The IDMC statistician re-calculated the sample size using this adjusted variance.

$$SSSSxxxxxx_{iiii} = \sum_{iiii=1}^{vvvv} (xxxx_{iiii} - \bar{xxxx})^2 = (mmmm - \bar{mmmm})^2 + (2mmmm - \bar{mmmm})^2 + \dots + (vvvvmmmm - \bar{mmmm})^2 = \frac{mmmm^2 vvvv(vvvv^2 - 1)}{12}$$

Thus,  $VVVV\beta\beta\beta\beta\beta\beta$  can be written as,

$$VVVV\beta\beta\beta\beta\beta\beta = 1 \cdot \sum_{iiii=1}^{vvvv} \frac{\sigma\sigma\sigma^2 ee^2}{SSSSxxxxxx_{iiii}} + \sigma\sigma\sigma^2 \bar{ee}^2 = \frac{2}{NNNN} \cdot \frac{\sigma\sigma\sigma^2}{SSSSxxxxxx_{iiii}} \pm \sigma\sigma\sigma^2 \bar{ee}^2 = \frac{2}{NNNN} \cdot \frac{\sigma\sigma\sigma^2}{\frac{mmmm^2 vvvv(vvvv^2 - 1)}{12}} + \sigma\sigma\sigma^2 \bar{ee}^2$$

Applying the same steps to drug treated patients, Fishers Information,  $IIIFFFF$ , expected at the end of the trial with  $NNNN$  patients followed for  $FFFF$  months is given by

where  $VVVV\beta\beta\beta\beta\alpha_{DD}$  and  $VVVV\beta\beta\beta\beta\alpha_{PP}$  are the variances of the estimated slope values for the drug and placebo groups, respectively.

Fisher's Information for the first N=180 patients, randomized over 45 months and followed for minimum follow-up of 9 months, is easily estimated in SAS to be  $III_{III} = 52.591$  such that the information fraction for eGFR slope would be  $52.591/107.175 = 49.1\%$ ; the associated SAS code for this computation is provided in [Appendix 3](#).

At the time of the primary endpoint analysis with  $N =$  the first 180 high-risk proteinuria patients, the available eGFR data will be analyzed via random coefficients modelling (Section 2.9.2.3) to provide an estimate of the difference in annualized eGFR rate of decline between narsoplimab and placebo,  $\beta_3 - \beta_4$ , along with its standard error,  $\text{SE}(\beta_3 - \beta_4)$ , as well as between slope and residual error variance component estimates,  $\text{SE}(\sigma_s^2)$  and  $\text{SE}(\sigma_e^2)$ . No p-value for the difference in annualized eGFR rate of decline will be generated. Denote the z-value for annualized eGFR rate of decline at the time of the primary endpoint analysis as,

$$zzzz_{\text{iii}} = \frac{\beta}{ssssss(\beta_3)_{\text{iii}}}$$

The CP of confirming a treatment effect on annualized eGFR rate of decline with the planned N = 280 randomized high-risk proteinuria patients followed for 24 months is calculated according to Mehta and Pocock (2011) as,

$$CCCCCCCC(zzzzzzz) = 1 - \Phi \frac{\diamond zzzzzzz \diamond IIIIFFFF - zzzzz \diamond IIII III}{\diamond IIIIFFFF - IIII III} - \frac{zzzz \diamond IIIIFFFF - IIIIII}{\diamond IIII III}$$

If the computed CP is < 85%, the sample size for the annualized eGFR rate of decline endpoint in the high-risk UPE group may be increased from the planned 280 patients up to a maximum of 360 patients to increase CP, with the recruitment period extended, if necessary. Note: should the sample size be increased in the high-risk proteinuria group up to a maximum of 360 patients, the all-patients population (i.e., all patients with baseline UPE > 1 g/day) will be approximately, N = 600 (assuming a ratio of high-risk proteinuria to non-high-risk proteinuria patient groups of 60:40).

To deliver a desired CP of  $1 - \beta$ , [Mehta 2011] have shown that the information post interim,  $(III_{FFFF} - III_{III})$ , should be increased to  $(III^{*}_{II} - III_{III})$  where,

$$\frac{III^* - III}{FFFF} = \frac{III^* - III}{\frac{zzzz_{\text{zzzz}} \cdot VVVV_{\text{FFFF}} - zzzz_{\text{zzzz}} \cdot VVVV_{\text{FFFF}}}{(zzzz_{\text{zzzz}})^2} - III}^2$$

The revised total sample size for the 2-year annualized eGFR rate of change endpoint in the high-risk proteinuria group will be  $NNNN^* = nnnn_{\text{nnnn}} + nnnn^*$ , with  $NNNN^* \in [280, 360]$  so that  $nnnn^* \in [280 - nnnn_{\text{nnnn}}, 360 - nnnn_{\text{nnnn}}]$  (i.e., the total sample size,  $NNNN^*$ , for the eGFR rate of change endpoint in the high-risk proteinuria group will not be permitted to be less than 280 patients).

The required  $NNNN^*$  to deliver the increase information content,  $II_{FF}II_{FF}^*$ , is computed via the relation

$$\{II_{FF}II_{FF}^*\}^{-1} = \frac{4}{SSSS_{\text{ssssssss}}} + 0000_{\text{0000}}^2$$

where  $SSSS_{\text{ssssssss}} = 378$  as per Section 1.3.2.

In order to avoid the potential for alpha inflation, data from pre and post the eGFR endpoint SSRE will be combined using the fixed weights approach described by [Cui 1999]. This approach guarantees alpha control regardless of mechanism for any increase in sample size. The approach fundamentally depends upon the long-established, basic properties of group sequential trial designs, being as follows:

- Assume two treatments, experimental (E) and control (C).
- The hypothesis to be tested for some parameter of interest,  $\theta$ , is  $H_0: \theta_{TTTTTTTTTTTTTT} = 0$  vs  $H_1: \theta_{TTTTTTTTTTTTTT} \neq 0$ .
- For the purposes of sizing, assume  $\theta_{TTTTTTTTTTTTTT} = \theta (>0)$  under the alternative.
- Let  $\theta\theta\theta$  be a sufficient statistic for  $\theta$  with distribution  $ffff(xxxx|\theta\theta\theta\theta) \sim NNNN(\theta\theta\theta\theta, VVVV^{-1})$ .
- Hence  $zzzz = \theta\theta\theta\sqrt{VVVV}$  with distribution  $ffff(zzzz|\theta\theta\theta\theta) \sim NNNN(\theta\theta\theta\theta, VVVV, 1)$ .
- Trial size is governed by Type I and Type II errors,  $\alpha$  and  $\beta$ , and the need to deliver the required Fishers Information content,  $VVVV = \frac{zzzz_{\alpha\alpha\alpha\alpha} + zzzz_{\beta\beta\beta\beta}}{\theta\theta\theta\theta^2}$ .
- $KKKK$  analyses planned with the  $iiii$  having information content  $VVVV_{iiii} = \frac{iii}{KKKK}$
- Then,
  - $\theta\theta\theta\theta_{1,..., \theta\theta\theta\theta_{KKKK}} \sim MMMMVVVVNNNN$  with  $\theta\theta\theta\theta_{iii} \sim NNNN(\theta\theta\theta\theta, VVVV^{-1})$  and  $cccccccvvv(\theta\theta\theta_{pppp}, \theta\theta\theta\theta_{mmmm}) = VVVV^{-1}$
  - $zzzz_{iiii} = \theta\theta\theta\theta_{iiii}\sqrt{VVVV_{iiii}}$  so that  $zzzz_{1,..., zzzz_{KKKK}} \sim MMMMVVVVNNNN$  with  $zzzz_{iii} \sim NNNN(\theta\theta\theta\theta, VVVV_{iiii}, 1)$  and  $cccccccvvv(zzzz_{pppp}, zzzz_{mmmm}) = \sqrt{VVVV_{pppp}/VVVV_{mmmm}}$
  - $SSSS_{iiii} = zzzz_{iiii}\sqrt{VVVV_{iiii}}$  so that  $SSSS_{1,..., SSSS_{KKKK}} \sim MMMMVVVVNNNN$  with  $\theta\theta\theta\theta_{iii} \sim NNNN(\theta\theta\theta\theta, VVVV_{iiii}, VVVV_{iiii})$  and  $cccccccvvv(SSSS_{pppp}, SSSS_{mmmm}) = VVVV_{pppp}$
  - $\theta\theta\theta_{1,..., \theta\theta\theta\theta_{KKKK}}, zzzz_{1,..., zzzz_{KKKK}}$  and  $SSSS_{1,..., SSSS_{KKKK}}$  ( $SSSS_{iiii}$  being score statistics) have a joint canonical distribution
  - Thus independent increments apply to the score statistics i.e.,  $SSSS_{iiii} - SSSS_{iiii-1} \sim NNNN(\theta\theta\theta\theta(VVVV_{iiii} - VVVV_{iiii-1}), \theta\theta\theta\theta(VVVV_{iiii} - VVVV_{iiii-1}))$  independently of  $SSSS_{1,..., SSSS_{iiii-1}}$

These properties directly apply in the case of a random coefficients analysis with

$$\begin{aligned}
 VVVV &= \frac{\sigma\sigma\sigma^2 e e e}{NNNN} + \sigma\sigma\sigma\sigma^{-1} \\
 VVV &= \frac{4}{\frac{NNNN}{iii}} \frac{\overbrace{\sigma\sigma\sigma^2}^{SSSSxxxxx}}{4} + \sigma\sigma\sigma\sigma^2 \frac{?}{bb} \\
 &\quad \frac{SSSSxxxxx}{xx}
 \end{aligned}$$

